11.2.4. Subject Disposition

The reasons for discontinuation will be collected when the subject's participation in the study ends and will be summarized by treatment group. The percentage of subjects discontinuing will be compared between groups. The median time to discontinuation will also be compared between treatment groups. The comparisons will be done for the overall percentage of subjects who discontinue and also for specific reasons for discontinuation.

11.2.5. Subject Characteristics

Baseline and demographic characteristics will be summarized by treatment group and overall. Summaries will be provided for continuous and categorical measures.

11.2.6. Prior and Concomitant Therapy

Prior medications are defined as those that stop before randomization. Concomitant medications are defined as those being taken on or after randomization. A summary of concomitant medications will be presented as frequencies and percentages for each treatment group. Fisher's exact test will be used to test for treatment differences between groups.

If the start or stop dates of therapies are missing or partial to the degree that determination cannot be made of whether the therapy is prior or concomitant, the therapy will be deemed concomitant.

Prior and concomitant medications will also be listed.

Medications will be coded using the World Health Organization drug dictionary.

11.2.7. Protocol Violations

Protocol violations will be analyzed as frequency tables between solanezumab and placebo. Listings of subjects with significant protocol violations will also be provided.

11.2.8. Analysis of Primary Outcome (Placebo-Controlled Period)

The primary objective of this study is to test the hypothesis that IV infusion of solanezumab will slow cognitive decline in preclinical AD as compared with placebo.

The original mITT analysis (that is, all participants as randomized to treatment who have a baseline and at least 1 postbaseline measure) for the primary outcome will be retained and conducted at the end of the treatment period, although the dose will be increased during the study; in other words, the primary analysis will include all data for the solanezumab group as the treatment group versus placebo. As with the original analysis plan, the hypothesis for this analysis will be tested against an alpha level of .05.

The details of this analysis including the analytic method and model are presented below.

An NCS analysis will be used to assess the difference between treatment groups in change from baseline for the PACC score at 4.5 years. The composite score at baseline and each post-baseline visit will be the dependent variable. Time will be treated as a continuous variable with values equal to years between baseline and follow-up exam dates. We will assume an unstructured covariance structure. The fixed effects will include the following terms: (i) NCS basis expansion terms (two terms), (ii) NCS basis expansion terms-by-treatment interaction (two terms), (iii) PACC test version administered, (iv) age, (v) education, (vi) APOE 4 carrier (yes/no), and (vii) baseline florbetapir cortical SUV_r. The model is constrained to not allow a difference between treatment group means at baseline.

The null hypothesis is that the treatment difference between solanezumab and placebo for the PACC score at 240 weeks is equal to zero. The primary analysis will be carried out in the mITT population that is randomized and has a baseline score and at least 1 postbaseline assessment. If the unstructured covariance structure matrix results in a lack of convergence, the following structures will be used in sequence:

- heterogeneous Toeplitz covariance structure
- heterogeneous autoregressive order 1 covariance structure
- heterogeneous compound symmetry covariance structure, and
- compound symmetry covariance structure.

The sensitivity analyses of the effect of dose change on clinical outcomes are included in Section [11.2.9.2](#).

11.2.9. Analysis of Secondary Outcomes (Placebo-Controlled Period)

11.2.9.1. Clinical Outcomes

Similar to the primary analysis, each of the secondary efficacy outcomes will be assessed using an NCS analysis. These secondary efficacy outcomes include MMSE, ADCS-ADL Prevention

Questionnaire, CDR-SB, CFI, and C3. For each secondary efficacy measure, the baseline score and scores at each post-baseline visit during the treatment period will be analyzed using NCS.

Also similar to the primary analysis, all data from all patients regardless of dose increase will be included for the solanezumab and placebo groups.

Each of the secondary efficacy outcomes will be assessed using an MMRM analysis. These secondary efficacy outcomes include MMSE, ADCS-ADL Prevention Questionnaire, CDR-SB, CFI, and C3. For each secondary efficacy measure, scores at each post-baseline visit during the treatment period will be analyzed using MMRM.

An additional MMRM analysis, termed a slopes analysis, will be conducted examining the change from baseline score on the PACC at each scheduled postbaseline visit. The slope analysis will treat time from randomization as a continuous variable.

11.2.9.2. Sensitivity Analyses

Sensitivity analyses of the effect of dose change on clinical outcomes will be conducted as noted in the SAP.

1. An MMRM analysis will be performed separately on the PACC and other clinical measures after censoring all observations after the dose increase. In other words, change from baseline for the clinical measure will be obtained only through the last available value prior to first dose escalation for each subject.

The null hypothesis is that the treatment difference between solanezumab and placebo for the PACC score is equal to zero. Since the timing (visit) of dose escalation will vary for each subject, a specific endpoint for comparison between treatment groups will not be available. Therefore, the hypothesis will be tested using the p-value obtained for the overall treatment effect.

2. Additionally, we will implement a sensitivity analysis to estimate the potential differences in the treatment effect for the original dose and the higher dose by modeling the effects of a time-varying dose indicator variable (with values placebo, low, and high). The time-varying dose indicator variable will be fitted as a separate variable to the ITT model of change from baseline on the primary measure (PACC) and other secondary measures.

The fixed effects in the model for the sensitivity analysis will be constructed as follows:

$$\text{Change from baseline} = \text{baseline score} + \text{dose} + \text{visit} + \text{dose-by-visit interaction} + \text{age} + \text{education} + \text{baseline cortical SUVr}$$

The coefficient for this new time-varying dose indicator variable will provide estimates to

compare and contrast all dose groups at the relevant time points at which the different doses were assigned.

3. Another sensitivity analysis will include the mean dose for each subject as a separate co-variable. The fixed effects in the model will be the following:

Change from baseline = baseline score + treatment + visit + treatment-by-visit interaction + age + education + baseline cortical SUVR + mean dose.

Additional sensitivity analyses will be included in the SAP.

11.2.9.3. Biomarker Outcomes

Analysis of Plasma. Change in plasma A β and P-tau, GFAP, and Neurofilament light chain after treatment will be compared between treatment groups. This analysis will be done separately for each plasma A β and P-tau parameter.

Analysis of vMRI Data. Change in vMRI data after treatment will be compared between treatment groups. This analysis will be done separately for each vMRI parameter.

Analysis of Amyloid PET Imaging. To provide further supporting evidence that solanezumab attenuates the underlying pathologic process in AD, the change in brain amyloid burden obtained using florbetapir PET imaging will be assessed. Parameters from various brain regions of interest as well as a composite brain measure will be compared between treatment groups.

Analysis of Cerebrospinal Fluid. To provide further supporting evidence that solanezumab attenuates the underlying pathologic process in AD, changes in CSF parameters, including total and free A β_{1-40} and A β_{1-42} species and total tau and P-tau peptides, GFAP Neurofilament light chain, will be compared between treatment groups.

11.2.10. Open-Label Period

When change from baseline is assessed, subjects will be included in the summary only if both a baseline and a postbaseline measure are available. For efficacy analyses (noninferiority and superiority analyses), the baseline will be the last non-missing observation collected prior to the initiation of treatment in the placebo-controlled period, generally, Visit 6.

Treatment group comparisons used in the statistical analysis will be the treatment group to which the subjects were randomized in the placebo-controlled period (subjects randomized to solanezumab [early start] versus patients randomized to placebo [delayed start]).

For analyses using MMRM, an unstructured covariance matrix will be used to model the within-patient variance–covariance errors. If the unstructured covariance matrix results in a lack of convergence, the heterogeneous Toeplitz covariance structure, followed by the heterogeneous autoregressive covariance structure, will be used. The Kenward–Roger approximation will be used to estimate the denominator degrees of freedom.

In the event that the primary contrast for the placebo-controlled period at 240 weeks is statistically significant, delayed-start analyses will proceed based on the methods described by Liu-Seifert and colleagues (2015). Several efficacy measures (PACC, ADCS-ADL Prevention Questionnaire, CDR-SB, C3, and CFI) will be analyzed separately using a noninferiority hypothesis in an MMRM model, in which the specific hypothesis is that the advantage of solanezumab treatment demonstrated in the placebo-controlled period is sufficiently maintained in the open-label period. This randomized/delayed-start analysis will assess whether solanezumab has a persistent effect on disease course. That is, the hypothesis is that subjects originally randomized to receive placebo and later switched to solanezumab at the start of the open-label period do not “catch up” to subjects originally randomized to receive solanezumab in the placebo-controlled period. This may be understood as a comparison of the treatment difference at the end of the placebo-controlled period with the treatment difference at the end of the open-label period.

The noninferiority margin for this hypothesis is specified as 50% of the treatment difference observed at the end of the placebo-controlled period. The hypothesis will be tested by constructing a 90% one-sided CI of the difference in LS means at the last visit in the open-label period. If the lower limit of the CI rules out the difference that would have been obtained if 50% of the observed difference had been lost, the disease progression for the treatment groups will be considered parallel, indicating that the treatment effect is independent of symptomatic effects. The interim noninferiority analysis of the PACC up to Week 336 in the open-label period will be considered the main efficacy analysis for the open-label period.

In addition to the noninferiority test, superiority of early-start subjects compared with delayed-start subjects at the 336-week analysis in the open-label period will also be assessed. The PACC, ADCS-ADL Prevention Questionnaire, CDR-SB, C3, and CFI will be analyzed.

11.2.11. Gatekeeping Strategy

Given continuing evolution in the field regarding assessment of clinical meaningfulness in a preclinical AD population, a formal gatekeeping strategy is not currently planned. If a gatekeeping strategy is used, it will be specified in an SAP before database lock.

11.2.12. Pharmacokinetic/Pharmacodynamic Analyses

The distribution of observed plasma solanezumab concentrations will be graphically compared to simulated solanezumab concentrations generated by a population PK model developed with data from previous Phase 3 trials. If warranted, the population PK model parameters may be updated by combining data from this study with that from previous Phase 3 studies and re-fitting the final model. The population PK model may be used to estimate exposure parameters (for example, plasma solanezumab area under the curve), if appropriate. As warranted, the relationship between exposure estimates and safety, biomarker, or efficacy outcomes may be investigated through graphical or other analyses.

To evaluate the potential impact of immunogenicity on solanezumab PK, plasma solanezumab concentrations from subjects with treatment-emergent immunogenicity will be plotted as a

function of time, along with mean plasma solanezumab concentrations in all subjects. The anti-solanezumab titer associated with each plasma solanezumab concentration will be indicated on the graph (for example, by assigning a different symbol to each titer level). A region representing the middle 90% of observed plasma solanezumab concentrations in all subjects will also be presented on the graph. If this graphical analysis demonstrates a trend in plasma solanezumab concentrations in subjects with treatment-emergent immunogenicity relative to the overall trial population, additional work may be performed to characterize this trend.

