7.1.4. Dose Escalation

All subjects will be escalated to a dose of 1600 mg Q4W according to amendment (d). After at least 2 infusions of 400 mg Q4W, subjects will be escalated to 800 mg Q4W for at least 2 infusions, and then 1600 mg Q4W until the conclusion of the treatment (Section 9.1).

At a minimum, the first 200 subjects (approximately 100 each in the solanezumab and placebo treatment groups) who receive the increased dose will be included in a dose escalation safety cohort to receive additional safety assessments and monitoring (described in Section 10.2.11) during dose escalation to monitor the safety of the higher doses.

Subjects who escalate dose after entry in the dose escalation safety cohort has been closed will receive safety monitoring as described in the main Study Schedule.

All subjects who are active in the study should be escalated to a dose of 1600 mg Q4W as described above. Subjects may be permitted to delay dose escalation at the investigator's discretion; this will not be considered a protocol deviation.

Additional site training will be provided to ensure appropriate implementation of the protocol modifications.

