9.1. Treatments Administered

This study was initiated as a comparison of solanezumab 400 mg compared with placebo. The active drug group was given an IV infusion of solanezumab 400 mg once every 4 weeks. The study protocol was amended to increase the dose; subjects will be escalated to 800 mg Q4W for at least 2 infusions, and then 1600 mg Q4W until the conclusion of the treatment, as described below (Table A4.1). Dosing should be once every 4 weeks; a minimum of 14 days between infusions is required.

Table A4.1. Treatment Regimens

Regimen	Dose from Visit 6 (Week 0) through Visit 65 (Week 236), Placebo-Controlled Period
Solanezumab	
 • 400 mg IV infusion every 4 weeks for at least 2 doses^a, and then: • 800 mg IV infusion every 4 weeks for at least 2 doses, and • 1600 mg IV infusion every 4 weeks through Week 236
Placebo	sterile saline solution (0.9% sodium chloride) IV infusion every 4 weeks (infusion volumes to increase accordingly with dose escalation paradigm as described in the operations manual)
Dose from Visit 66 (Week 240) through Visit 116 (Week 440), Open-Label Period	
Early-start solanezumab ^b	1600 mg IV infusion every 4 weeks through Week 440 ^c
Delayed-start solanezumab ^b	
 • 400 mg IV infusion every 4 weeks for at least 2 doses^{a, c}, • 800 mg IV infusion every 4 weeks for at least 2 doses^c, and • 1600 mg IV infusion every 4 weeks through Week 440^c

Abbreviation: IV = intravenous.

^a Subjects who initiated the study before the implementation of amendment (d) may have more than 2 doses of 400 mg Q4W.

^b “Early-start solanezumab” refers to the treatment regimen received by subjects randomized to solanezumab in the placebo-controlled period who continue to receive solanezumab in the open-label period. “Delayed-start solanezumab” refers to the treatment regimen received by subjects randomized to placebo in the placebo-controlled period who switch to solanezumab treatment in the open-label period.

^c Subjects who are receiving 400 mg Q4W or 800 mg Q4W when they complete the placebo-controlled period may be maintained at that dose in the open-label period.

Changes in the escalation schedule may be made at the investigator’s discretion with the notification of a Medical Monitor.

The investigator or his/her designee is responsible for the following:

- Explaining the correct use of the investigational agent(s) to the site personnel

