Phase 2 solanezumab data suggest greater central target engagement may be achieved with dosing greater than 400 mg Q4W. A dose of 400 mg every week (400 mg QW), which is equivalent to 1600 mg over a 4-week period, was given in Phase 2 Studies LZAJ and LZAK, and showed an increased CSF A β signal and an acceptable safety profile.

Exposure–response analyses were conducted following the completion of Studies LZAM, LZAN, and LZAX, but given that only a single dose level was administered in these studies, no compelling relationship between exposure and change in various cognitive endpoints could be discerned.

Biomarker data from patients receiving LPs in Studies LZAM, LZAN, and LZAX suggest that the effect of solanezumab on A β_{1-40} and A β_{1-42} species in the CNS (central target engagement) was present but relatively modest in those studies. Total A β concentrations tended to increase with increasing solanezumab concentrations in the CSF, without reaching an apparent plateau, suggesting that higher solanezumab exposures in the CNS would lead to higher levels of target engagement. Indeed, total A β_{1-40} and A β_{1-42} concentrations were observed to be substantially higher, with a dose of 400 mg QW examined after 12 weeks of dosing in the Phase 2 Study LZAJ, as compared with the Q4W dosing regimen.

To date, the pharmacokinetics (PK) of solanezumab have been explored in single doses up to 10 mg/kg (approximately 700 mg), or multiple doses of up to 400 mg QW. The PK of solanezumab have been linear with respect to dose, and stationary with respect to time. Accordingly, the average plasma solanezumab concentration over 4 weeks at a dosing regimen of 1600 mg Q4W would be anticipated to be equivalent to the exposure over 4 weeks at the previously tested 400 mg QW dosing regimen. This projected exposure is less than the no-observed-adverse-effect level (NOAEL) exposure determined in monkeys as part of a 12-month chronic toxicology study. Assuming linear PK, the projected C_{max} at 1600 mg Q4W is anticipated to provide an exposure multiple that is similar to that calculated for the projected average concentration.

Solanezumab was well tolerated in monkeys, with no adverse effects observed at the maximum dose studied, 100 mg/kg. Solanezumab exposures at 1600 mg Q4W were projected using

clinical data collected at 400 mg Q4W. These exposure estimates provide a 5.8X multiple to the exposures in monkeys at the 100 mg/kg dose.

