10.1.3.2. Plasma Solanezumab

Plasma will be collected from all subjects for determination of plasma solanezumab concentration. Not all of these samples will be assayed for solanezumab concentration. It is intended that plasma solanezumab concentrations will be determined for approximately the first 200 subjects to complete the study. In addition, plasma solanezumab concentrations will be determined for any subject who also has positive anti-solanezumab titers. Plasma concentrations from other subjects may be determined as warranted.

Plasma concentrations of solanezumab and $A\beta$ species for pharmacodynamic analysis may be determined from processed blood samples using validated immunoassay and/or mass spectrometry methods. Analysis of $A\beta$ species is intended to confirm the solanezumab pharmacodynamic effect (the "peripheral sink" effect) hypothesized to enhance $A\beta$ clearance from the CNS to the peripheral circulation. Other plasma $A\beta$ species thought to be associated with amyloid plaque may also be analyzed.

Samples from placebo-treated subjects will not be assayed for solanezumab. Results that could unblind the study will not be reported to investigative sites or other blinded personnel.

Sample collection, handling, and shipment will occur according to the procedures described in the relevant procedures manual.

Bioanalytical samples collected to measure investigational product concentration will be retained for a maximum of 1 year after all subjects complete the study (that is, the last subject's visit).

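### The antibody–PK graph compares antibody-positive participants with one all-dose mean and 90% region, so at visits where doses are mixed it can hide a halved concentration on 1600 mg

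*Protocol*

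**What the plan says.** Protocol 11.2.12 plots concentrations from subjects with treatment-emergent immunogenicity against time, "along with mean plasma solanezumab concentrations in all subjects", and adds one range: "A region representing the middle 90% of observed plasma solanezumab concentrations in all subjects will also be presented on the graph". The titer at each point may be shown by symbol; dose is not mentioned. Follow-up is conditional and optional: "If this graphical analysis demonstrates a trend in plasma solanezumab concentrations" relative to the trial as a whole, more work may be done.

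Several other provisions bear on this reference:

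- **Dose levels.** Section 7.1.4: "After at least 2 infusions of 400 mg Q4W, subjects will be escalated to 800 mg Q4W for at least 2 infusions", then 1600 mg.
- **Overlap in time.** Table A4.1, footnote a (Section 9.1): "Subjects who initiated the study before the implementation of amendment (d) may have more than 2 doses of 400 mg Q4W". Section 7.1.4 adds: "Subjects may be permitted to delay dose escalation at the investigator's discretion".
- **Dose proportionality.** Section 9.4: "The PK of solanezumab have been linear with respect to dose, and stationary with respect to time".
- **Who is assayed.** Section 10.1.3.2 names about the first 200 completers, and "plasma solanezumab concentrations will be determined for any subject who also has positive anti-solanezumab titers". Others may be assayed if warranted. Placebo samples are not assayed, so in practice the all-subject reference consists of solanezumab participants at whatever dose they were on.

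The SAP has no PK section. SAP 7.13.6.2 lists concentrations beside antibody results, without a reference range by dose.

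**The concern.** A single mean and range work as a reference when everyone is on one dose. Here the expected concentration at a given week can differ fourfold for reasons unrelated to antibodies.

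The schedule makes this mixing likely. On the minimum escalation, a participant receives 400 mg at Weeks 0 and 4, 800 mg at Weeks 8 and 12, and 1600 mg from Week 16. Attachment 1 schedules plasma for solanezumab, drawn before the infusion, at Weeks 0, 12, 24, 48, 108, 168 and 240. At Week 24 that participant is on 1600 mg, while one enrolled before amendment (d) may still be on 400 mg.

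The pooled range then covers several doses. A real fall in exposure on 1600 mg can sit inside it, and an unaffected participant on 400 mg can sit below it. At stake is the stated check on whether antibodies lower exposure, and whether any follow-up of that question starts. The primary efficacy test is not affected.

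**Working it through.** The documents give no operating characteristics for this graph, so there is no figure to reproduce.

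**Inputs from the documents.** Doses of 400, 800 and 1600 mg with linear PK give relative medians of 0.25, 0.50 and 1. The reference region is the 5th to 95th percentile of all values.

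**Assumptions, because the documents are silent.** Concentrations are log-normal with a between-subject CV of 30% to 60%. The share *p* of values at 400 mg is varied, with the rest at 1600 mg.

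**Formulas.** σ = √ln(1 + CV²), which is 0.294 at CV 30% and 0.555 at CV 60%. The pooled lower limit L solves

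p·Φ(ln(L/0.25)/σ) + (1 − p)·Φ(ln(L)/σ) = 0.05.

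The chance that a 1600 mg concentration multiplied by f falls below it is Φ(ln(L/f)/σ).

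**Worked case, CV 30%.**

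- 1600 mg-only region: L = exp(−1.645 × 0.294) = 0.617. A halved value falls below with probability Φ(ln(0.617/0.5)/0.294) = Φ(0.72) = 76%.
- Pooled, p = 10%: L = 0.25 satisfies the equation, since 0.10 × 0.5 + 0.90 × Φ(−4.7) ≈ 0.05. A halved value falls below with probability Φ(ln(0.25/0.5)/0.294) = Φ(−2.36) = 0.9%.

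**Results (first figure CV 30%, second CV 60%).**

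| Share at 400 mg | Lower limit | Halved 1600 mg value below | Unaffected 400 mg value below |
|---|---|---|---|
| 0% (1600 mg only) | 0.62 / 0.40 | 76% / 35% | – |
| 3% | 0.55 / 0.35 | 63% / 26% | 99.6% / 73% |
| 5% | 0.43 / 0.31 | 29% / 20% | 97% / 66% |
| 10% | 0.25 / 0.24 | 0.9% / 8.8% | 50% / 46% |
| 50% | 0.17 / 0.12 | 0.01% / 0.6% | 10% / 10% |

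At an even mix the upper-to-lower ratio of the region is 8.5 to 16.6, against 2.6 to 6.2 within one dose. A 60% loss on 1600 mg then falls below the pooled limit 0.2–1.7% of the time, against 50–93% for a dose-specific limit. A 90% loss falls below it 97% (CV 30%) to 64% (CV 60%) of the time.

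Adding some values at 800 mg changes little. With 10% at 400 mg and 5% at 800 mg, the lower limit at CV 30% is 0.249.

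**Limit of any dose-specific region.** Its lower limit reaches 0.5 when CV is about 44%. Above that, the median halved value lies inside even a 1600 mg-only region.

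**The case against.** The strongest reply is that the graph is descriptive and the harm conditional.

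- **Visit mix.** A reader might infer that a halved 1600 mg level would look normal throughout. That does not follow. The plot is against time, and Section 7.1.4 expects all active subjects to escalate. With 97% of values at 1600 mg and CV 30%, 63% of halved values fall below the pooled limit, against 76% with a dose-specific one. This stands.
- **The mean.** A reader might infer that affected 1600 mg values would lie above the mean. At an even mix they lie below it 75–82% of the time, against 7–28% of unaffected 1600 mg values, so that reading needs a reference drawn mostly from 400 mg. This stands too. But at the same mix Φ(ln(0.653/0.25)/0.294) = 99.9% (CV 30%) and Φ(ln(0.729/0.25)/0.555) = 97% (CV 60%) of unaffected 400 mg values also lie below the mean. Without dose marking, position against the mean does not separate antibody effect from dose.
- **Reference group.** A reader might take it to be 400 mg only, since first completers probably enrolled early. Section 10.1.3.2 allows other subjects to be assayed, and Section 10.2.11.4 adds samples on 800 and 1600 mg in the escalation safety cohort, so that is an extreme case.
- **Other material.** Individual time courses with titer allow some comparison with a participant's own earlier values. SAP 7.13.6.2 lists concentrations, Protocol 11.2.12 separately compares observed with simulated concentrations, and Protocol 11.2.13 splits safety analyses by dose. These give partial help; none supplies a dose-appropriate reference for this graph.

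**Conclusion.** The point holds in a limited form. Section 11.2.12 specifies a reference that ignores dose in a trial where dose varies fourfold, and nothing in the SAP corrects it. At visits where about 10% or more of values come from 400 mg, the pooled region flags fewer than about 9% of halved 1600 mg concentrations, against about 35–76% for a dose-specific region. It also flags unaffected 400 mg participants too often: about 10% at an even mix and 46–50% when 10% of values are at 400 mg, against a nominal 5%.

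These sizes rest on log-normal concentrations, the stated linear PK, an assumed CV of 30–60% and assumed dose shares. The masking fades at visits with about 95–97% or more of values at 1600 mg, although at 95% detection of a halved value is still only 20–29%. Very large losses would usually still show.

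The documents do not support the broader reading that the graph fails at every visit, or that the whole conclusion on immunogenicity and PK rests on it. It is an exploratory display whose only stated consequence is optional further work. The change is still worth making because it is small.

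**What to change.** In Protocol 11.2.12, or the PK analysis plan that implements it, choose one of three references:

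- concentrations divided by the dose level in effect, relying on the stated linear PK;
- observed/predicted ratios from the population PK model the section already plans to use;
- the mean and 90% region drawn separately by dose level in effect at sampling.

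Draw the mean and region on the chosen scale, and mark dose alongside titer at each point.

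The cost is about one sentence of analysis text, with no new samples or assays. There are two drawbacks. Samples taken just after a dose step reflect more than one dose, so they need model prediction or must be left out of the simple dose-normalised plot. At high CV even a dose-specific region will miss some halved concentrations. The change concerns the display only and implies nothing about which dose is appropriate.
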